5.4 Stratification

A total of up to 62 eligible patients will be enrolled on this trial (up to 30 melanoma patients who are anti-PD-1/PD-L1-experienced and up to 32 RCC patients who are anti-PD-1/PD-L1-experienced). Individual cohorts of the study can be stopped for futility according to a Simon two-stage design. The study will accrue for approximately 36 months and will be open for approximately 24 additional months as patients on study are treated and followed.

5.5 Concomitant Medications/Vaccinations/Therapies (allowed & prohibited)

Medications or vaccinations specifically prohibited in the exclusion criteria are not allowed during the ongoing trial. If there is a clinical indication for one of these or other medications or vaccinations specifically prohibited during the trial, discontinuation from trial therapy or vaccination may be required. The final decision on any supportive therapy or vaccination rests with the investigator and/or the participant's primary physician.

5.5.1 Acceptable Concomitant Medications

All treatments that the investigator considers necessary for a participant's welfare may be administered at the discretion of the investigator in keeping with the community standards of medical care. All concomitant medication will be recorded on the case report form (CRF) including all prescription, over-the-counter (OTC), herbal supplements, and IV medications and fluids. If changes occur during the trial period, documentation of drug dosage, frequency, route, and date may also be included on the CRF.

All concomitant medications received within 28 days before the first dose of trial treatment and 30 days after the last dose of trial treatment should be recorded. Concomitant medications administered after 30 days after the last dose of trial treatment should be recorded for SAEs and ECIs as defined in Section 7.2.

5.5.2 Prohibited Concomitant Medications

Participants are prohibited from receiving the following therapies during the Screening and Treatment Phase (including retreatment for post-complete response relapse) of this trial:

- Antineoplastic systemic chemotherapy or biological therapy
- Immunotherapy not specified in this protocol
- Chemotherapy not specified in this protocol
- Investigational agents other than pembrolizumab and lenvatinib
- Radiation therapy
 - Note: Radiation therapy to a progressing, symptomatic solitary intracranial or extracranial lesion may be allowed after consultation with the study PI. Radiation to an intracranial lesion must be given at least 7 days prior to the initiation of study drugs. Palliative radiation to other sites may be administered at any time.
- Live vaccines within 30 days prior to the first dose of study treatment and while participating in the study. Examples of live vaccines include, but are not limited to, the following: measles, mumps, rubella, varicella/zoster, yellow fever, rabies, BCG, and typhoid vaccine. Seasonal influenza vaccines for injection are generally killed virus vaccines and are allowed; however, intranasal influenza vaccines (eg, FluMist®) are live attenuated vaccines and are not allowed.
- Systemic glucocorticoids for any purpose other than to modulate symptoms from an event of clinical interest of suspected immunologic etiology. The use of physiologic doses of corticosteroids (doses ≤ 10 mg prednisone daily or equivalent) is approved.

Participants who, in the assessment by the investigator, require the use of any of the aforementioned treatments for clinical management should be removed from the study. All treatments that the Investigator considers necessary for a participant's welfare may be administered at the discretion of the Investigator in keeping with the community standards of medical care.

Medications or vaccinations specifically prohibited in the exclusion criteria are not allowed during the ongoing study. If there is a clinical indication for any medication or vaccination specifically prohibited during the study, discontinuation from study therapy or vaccination may be required. The final decision on any supportive therapy or vaccination rests with the investigator and/or the participant's primary physician. However, the decision to continue the participant on study treatment requires the mutual agreement of the investigator, the study PI and the participant.

There are no prohibited therapies during the Post-Treatment Follow-up Phase.

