Based on our institutional experience with the aforementioned trial of pembrolizumab in patients with brain metastases, perilesional cerebral edema can limit the ability to administer the drug (Kluger et al., 2019). Moreover, it can require steroid administration, theoretically hampering the activity of immune therapy. Additionally, prior local therapy with SRS can be complicated by radiation necrosis, particularly in patients receiving immune checkpoint inhibitors (Colaco, Martin, Kluger, Yu, & Chiang, 2016). Bevacizumab, an antibody to vascular endothelial growth factor (VEGF), has been shown to reduce cerebral perilesional edema (Torcuator et al., 2009). Additionally, single agent antiangiogenic therapy has minimal activity in melanoma; cabozantinib (Daud et al., 2017), ramucirumab (Carvajal et al., 2014), and aflibercept (Tarhini et al., 2011) have had modest activity in phase 2 trials. A number of lines of pre-clinical evidence support synergistic effects of immune checkpoint inhibitors combined with inhibitors of the VEGF pathway. VEGF decreases dendritic cell function and subsequently antigen presentation and T cell activation while promoting the development of myeloid-derived suppressor cells (Gabrilovich, Ishida, Nadaf, Ohm, & Carbone, 1999; Ohm & Carbone, 2001). VEGF is commonly found in the tumor microenvironment where it functions in immune evasion by altering the tumor vasculature to reduce lymphocyte adhesion to vessel walls, thus contributing to decreased trafficking across endothelium into tumor deposits (Bouzin, Brouet, De Vriese, Dewever, & Feron, 2007; Kandalaft, Motz, Busch, & Coukos, 2011; Ozao-Choy et al., 2009). Restoration of dendritic cell and T cell function may improve the T cell response and result in overall improved clinical activity (Hodi et al., 2014; Kandalaft et al., 2011).

Lenvatinib has shown clinical activity in RCC in the TKI refractory setting in combination with everolimus (Motzer, Hutson, et al., 2015) and in an early phase clinical trial in combination with pembrolizumab (Taylor et al., 2020), and thus makes the combination of pembrolizumab plus lenvatinib worthy of study for RCC brain metastases.

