5.5.4 Local Therapy and Treatment Beyond Disease Progression

Local therapy for brain metastases:

Local therapy in the form of craniotomy, LITT, or SRS can be performed on symptomatic brain lesions prior to assessment for study eligibility, provided all neurologic side effects from the procedure have resolved and all other eligibility criteria are met. At any time point throughout the study, local therapy (surgery, LITT, or SRS) will be administered to a lesion that becomes clinically concerning if deemed necessary by the investigators. This can be followed by continuation on pembrolizumab and lenvatinib, provided that the patient is otherwise benefiting from therapy and has stable disease or disease shrinkage in other lesions by RECIST criteria. Approval from the study PI or co-PIs is required to continue treating the patient on pembrolizumab and lenvatinib. Craniotomy and LITT are considered major procedures and require temporary holding of lenvatinib as detailed in Section 5.2.2.15. SRS is considered a minor procedure and does not require holding of lenvatinib. Further details for holding lenvatinib are detailed in Section 5.2.2.15.

A brain metastasis that has been treated locally will not be considered evaluable for response and will not be included when calculating the sum of largest dimensions. If the treated lesion constitutes >25% of the target lesions (for example, if one of three target lesions is treated locally), this will be considered progressive disease. If >75% of the baseline lesions are not treated with local therapy and evaluable by imaging, the patient will be considered evaluable, and response for the primary endpoint analysis will be assessed based on the remaining lesions. Additional response evaluation will be performed which will consider those patients who require local therapy while on study as having PD at the time of local therapy.

Local therapy for extra-cerebral metastases:

Local surgery or radiation therapy (if indicated for palliative measures only after discussion with the study PI or co-PIs) may be permitted and the patient can continue to receive pembrolizumab and lenvatinib provided there is otherwise evidence of clinical benefit from treatment (i.e. stable disease or response in measurable lesions). The criteria applied for assessing response is detailed in Section 7.1.2.9.

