5.6 Participant Withdrawal/Discontinuation Criteria

Discontinuation of study intervention does not represent withdrawal from the study.

As certain data on clinical events beyond study intervention discontinuation may be important to the study, they must be collected through the participant's last scheduled follow-up, even if the participant has discontinued study intervention. Therefore, all participants who discontinue study intervention prior to completion of the protocol-specified treatment period will still continue to participate in the study as specified in Section 7.1.4.

Participants may discontinue study intervention at any time for any reason or be discontinued from the study intervention at the discretion of the investigator should any untoward effect occur. In addition, a participant may be discontinued from study intervention by the investigator or the study PI if study intervention is inappropriate, the study plan is violated, or for administrative and/or other safety reasons. Specific details regarding procedures to be performed at study intervention discontinuation are provided in Section 7.1.5.3.

A participant must be discontinued from study treatment but continue to be monitored in the study for any of the following reasons:

- The participant or participant's legally acceptable representative requests to discontinue study treatment.
- Confirmed radiographic disease progression outlined in Section 7.1.2.9. Patients who are believed to be deriving benefit based on the discretion of the investigator and PI are allowed to continue.
- Any progression or recurrence of any malignancy, or any occurrence of secondary malignancy that requires active treatment. Exceptions to secondary malignancy include basal cell carcinoma of the skin, squamous cell carcinoma of the skin, new non-ulcerated primary melanoma <1 mm in depth with no nodal involvement, or carcinoma in situ (eg, breast carcinoma, cervical cancer in situ) that have undergone potentially curative therapy. Exceptions should be discussed with the study PI prior to continuing therapy or remaining in follow-up.
- Unacceptable adverse experiences as described in Section 5.2.2.

- The participant has a medical condition or personal circumstance which, in the opinion of the investigator and/or sponsor, placed the participant at unnecessary risk from continued administration of study treatment.
- The participant has a confirmed positive serum pregnancy test.

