A participant must be withdrawn from the study if the participant or participant's legally acceptable representative withdraws consent from the study.

If a participant withdraws from the study, they will no longer receive study treatment or be followed at scheduled protocol visits.

Specific details regarding procedures to be performed at the time of withdrawal from the study, are outlined in Section 7.1.4. The procedures to be performed should a participant repeatedly fail to return for scheduled visits and/or if the study site is unable to contact the participant are outlined below.

Lost to Follow-up

If a participant fails to return to the clinic for a required study visit and/or if the site is unable to contact the participant, the following procedures are to be performed:

- The site must attempt to contact the participant and reschedule the missed visit. If the participant is contacted, the participant should be counseled on the importance of maintaining the protocol-specified visit schedule.
- The investigator or designee must make every effort to regain contact with the participant at each missed visit (eg, telephone calls and/or a certified letter to the participant's last known mailing address or locally equivalent methods). These contact attempts should be documented in the participant's medical record.
- Note: A participant is not considered lost to follow-up until the last scheduled visit for the individual participant. The missing data for the participant will be managed via the prespecified statistical data handling and analysis guidelines.

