8.3 Statistical Analysis Plan

This section outlines the statistical analysis strategy and procedures for the study. If after the study has begun, changes are made to primary and/or key secondary hypotheses, or the statistical methods related to those hypotheses, then the protocol will be amended (consistent with ICH Guideline E9).

All baseline patient demographics and clinical characteristics will be summarized by mean/standard deviations and count/frequency for continuous and categorical variables respectively. All analyses will be completed as intent to treat.

Intracranial and Objective Response Rate

The primary endpoint is the best brain metastasis response rate of pembrolizumab in combination with lenvatinib. For the primary objective, the proportion of patients that experienced an intracranial response in each cohort will be estimated with corresponding 95% confidence interval.

The combination will be deemed worthy of further study as outlined in the Simon 2-stage designs in Section 8.2.

For objective response rate, the proportion of patients experience an objective response in each cohort will be estimated with corresponding 95% confidence interval.

PFS and OS

The non-parametric Kaplan-Meier method will be used to estimate median survival, along with survival at 1 year and 2 years.

Participants without documented event at the time of analysis will be censored at the date of last clinical evaluation for each outcome.

Duration of Intracranial Response Analysis

Duration of intracranial response will be evaluated by the Kaplan-Meier method. Intracranial responses will be analyzed separately from extracranial responses. If the patient has SD/PR/CR in the brain but PD in the body, then the patient will still be considered to have an ongoing intracranial response.

Statistical Methods for Safety Analyses

AEs will be coded using the standard Medical Dictionary for Regulatory Activities (MedDRA) and grouped system organ class. AEs will be graded by the investigator according to the NCI CTCAE, v5.0.

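### Section 5.5.2 takes participants who need a prohibited treatment off the study, against the follow-up rules in 5.6 and 7.1.5.3; read literally, it risks informative censoring

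*Combined protocol and SAP*

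**What the plan says.** Section 5.5.2 lists therapies prohibited during screening and treatment. The list includes other anticancer therapy, radiation (with exceptions) and "Systemic glucocorticoids for any purpose other than to modulate symptoms from an event of clinical interest of suspected immunologic etiology"; physiologic doses, up to 10 mg prednisone daily or equivalent, are accepted. It then says that participants who, in the investigator's assessment, "require the use of any of the aforementioned treatments for clinical management should be removed from the study".

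The same section later uses softer wording: a clinical need for a prohibited drug may require stopping study therapy, and treatment may continue if the investigator, the study PI and the participant agree. It closes by saying that nothing is prohibited in post-treatment follow-up.

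Section 5.6 separates the two concepts: "Discontinuation of study intervention does not represent withdrawal from the study". It requires data collection through the last scheduled follow-up after treatment stops. Its only mandatory ground for leaving the study is withdrawal of consent, with this consequence: "If a participant withdraws from the study, they will no longer receive study treatment or be followed at scheduled protocol visits".

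Sections 7.1.5.3.2 and 7.1.5.3.3 provide imaging every 12 weeks after stopping for a reason other than progression, and survival calls every 12 weeks after confirmed progression or new anticancer therapy.

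For PFS and OS, section 8.3 states: "Participants without documented event at the time of analysis will be censored at the date of last clinical evaluation for each outcome". It has no rule for participants removed under 5.5.2.

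**The concern.** The removal sentence speaks of the study, not of study treatment, and it is the only sentence that names these participants. The section 5.6 reasons for stopping treatment while staying under observation do not list need for a prohibited therapy.

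The trigger is related to prognosis. Section 4.2.1 says of perilesional oedema: "Moreover, it can require steroid administration, theoretically hampering the activity of immune therapy". Oedema and radiation necrosis are also the neurologic events singled out in 4.2.3.1 and in the fourth secondary hypothesis (3.2). A participant whose brain disease worsens enough to need steroids could therefore leave observation for that reason. Kaplan-Meier estimation assumes that censored patients have the same later risk as those who remain. Here their risk would probably be higher, and survival would be overstated. The efficacy analyses are by intention to treat, but that does not repair the problem: it keeps the patient in the analysis set without supplying the missing follow-up.

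**Working it through.** **1. The plan's own figures.** None bears directly on this point. The Simon designs were checked as background, with P(reject) = Σ over x1 > r1 of b(x1; n1, p) × P(X2 ≥ r + 1 − x1), where r + 1 is the number of responses needed to reject.

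- Melanoma (stop at 0/13; reject at 4 or more of 27): 0.0416 at p = 5%, 0.801 at p = 20%.
- RCC (stop at 2 or fewer of 18; reject at 7 or more of 29): 0.0497 at p = 12%, 0.801 at p = 30%. The 12% null is assumed from the cited nivolumab rate; section 8.2 does not label it as the null.

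Both meet the stated 80% power and 0.05 level. Neither calculation uses the removal sentence.

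**2. The texts side by side.**

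| Situation | Removal sentence in 5.5.2 | Other text |
|---|---|---|
| New anticancer therapy | Off study | Survival follow-up (7.1.1.5.3, 7.1.5.3.3) |
| Confirmed progression | Not a trigger in itself | Survival follow-up (7.1.5.3.3) |
| Local therapy to a worsening brain lesion | Radiation is listed, with a PI exception for a solitary lesion | Allowed at any time on study; drugs may continue with PI or co-PI approval (5.5.4) |
| Steroids above 10 mg for tumour-related oedema, no progression | Off study, no exception | Imaging follow-up (7.1.5.3.2), but only if removal is read as stopping treatment |

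The last row is where the contradiction matters most. Separately, the radiation note in 5.5.2 puts intracranial radiation at least 7 days before study drugs, while 5.5.4 allows radiosurgery during the study. Those passages must also be reconciled.

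**3. Size if 5.5.2 is applied literally.** The documents give no removal rate and no survival figure for these participants, so every input is an assumption. Other patients have exponential OS with median 12 months. A fraction f has median m months and is removed, if still alive, at a time uniform on months 1 to 4, with no contact afterwards. There is no other censoring.

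- True S(12) = (1 − f) × 2^(−12/12) + f × 2^(−12/m).
- Kaplan-Meier limit = exp{−∫ h(t) dt from 0 to 12}, with h(t) = [(1 − f)λ0S0 + fλ1S1G] / [(1 − f)S0 + fS1G]. Here S0 and S1 are the two exponential survival functions, λ0 = ln2/12 and λ1 = ln2/m. G(t) is the probability of not yet being removed: 1 before month 1, (4 − t)/3 to month 4, then 0.

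Example for the true value, f = 20%, m = 4: 0.8 × 0.5 + 0.2 × 0.125 = 42.50%.

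| m (months) | f | True 1-year OS | Kaplan-Meier reads | Bias (points) |
|---|---|---|---|---|
| 4 | 10% | 46.25% | 48.75% | +2.50 |
| 4 | 20% | 42.50% | 47.45% | +4.95 |
| 4 | 30% | 38.75% | 46.10% | +7.35 |
| 6 | 10% | 47.50% | 49.32% | +1.82 |
| 6 | 20% | 45.00% | 48.62% | +3.62 |
| 6 | 30% | 42.50% | 47.88% | +5.38 |

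**4. Sensitivity to the assumptions.** Suppose instead that the whole fraction survives to month 3, is removed then, and has a median of 3 further months. Kaplan-Meier reads [(1 − f) × 2^(−3/12) + f] × 2^(−9/12); the truth is (1 − f) × 0.5 + f × 2^(−9/3). For f = 10%, 20% and 30% this gives 50.9%, 51.9% and 52.8% against 46.3%, 42.5% and 38.8%, a bias of about 5, 9 and 14 points. The sign is stable; the size depends heavily on the assumptions.

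**5. If 5.6 is followed,** G(t) = 1 throughout, the Kaplan-Meier limit equals the true value, and the bias is zero.

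**6. Scale.** In a cohort of 27, 10% to 30% is 2.7 to 8.1 patients. The standard error of a 1-year rate near 42.5% is √(0.425 × 0.575/27) = 9.5 points, so the biases in step 3 are below one standard error of one cohort's estimate.

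**The case against.** The strongest reply is that the removal sentence is loose drafting and the rest of the protocol shows what is meant. Much of this stands. The sentence on loss of protocol visits in 5.6 concerns a participant who withdraws, and withdrawn consent is the only mandatory ground given. Permitting any therapy in post-treatment follow-up presupposes that such patients are still followed. Adverse events present at discontinuation or withdrawal are followed (7.1.4), and those above Grade 1 are followed to Grade 0-1 or new anticancer therapy (7.1.5.3.1). Oedema judged to be of suspected immune origin falls under the steroid exemption.

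Two stronger readings are therefore not supported. A reader might infer that radiation for a worsening brain lesion means removal. The note in 5.5.2 says "Radiation therapy to a progressing, symptomatic solitary intracranial or extracranial lesion may be allowed after consultation with the study PI", and after local therapy 5.5.4 says "This can be followed by continuation on pembrolizumab and lenvatinib, provided that the patient is otherwise benefiting from therapy". A reader might also infer that PFS, OS and CNS-toxicity data are bound to be lost in the sickest patients. The follow-up provisions point the other way, and oedema that led to steroids should already be a recorded adverse event.

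What the reply does not remove is the conflict itself. A patient needing steroids for tumour-related oedema, without progression or new anticancer therapy, reaches the imaging schedule only through one of two available readings. This is a multicentre trial, and sites could choose differently.

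**Conclusion.** The point holds as an unresolved contradiction that creates a risk of informative censoring. Under literal use of 5.5.2, OS would be biased upward: about 2 to 7 points at 1 year with 10% to 30% in the removal group and a median OS of 4 to 6 months there against 12 months in others, and more under harsher assumptions. PFS could also be affected, but no size is claimed: some deterioration is itself a progression event, and imaging follow-up already ends at new anticancer therapy (7.1.2.9.2, 7.1.5.3.2). The figures are a conditional illustration, not an estimate of what will happen. Under 5.6 there is no such loss, and the primary decision rules are unaffected. The point merits correction because the direction of the bias is predictable, follow-up missed at a site may not be recoverable, and the remedy is small.

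**What to change.** Amend the sentence in 5.5.2 to say that, when a prohibited treatment is needed, study treatment is handled as reconciled with 5.5.4 and 5.6, and the participant stays in the study for imaging, adverse-event and survival follow-up under 5.6 and 7.1.5.3. Reserve removal from the study for withdrawal of consent. In the same amendment, reconcile the 5.5.2 note on the timing of intracranial radiation with 5.5.4. Which treatments are permitted, and whether study treatment stops, is for the sponsor to settle; nothing here proposes a clinical rule.

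It would help to add a line to 8.3 saying how any participant whose follow-up nevertheless ended under 5.5.2 is handled in the PFS and OS analyses. The core cost is one amended sentence; the follow-up visits already exist, and the sample size does not change.
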